## **Protocol**

	Fe	lle	ow	:		,	MD
--	----	-----	----	---	--	---	----

Fellowship site: Stanford University

Fellowship Director: , MD MS

Additional Research Mentors:MD MPH;MD MSH;MD MSHP;, MD MS;

Project Title: Transcervical Balloon compared to Osmotic Dilators prior to Surgical Abortion: a Non-Inferiority Randomized Trial

We will conduct an unblinded, randomized, non-inferiority trial of 40 participants undergoing second trimester abortion between 18 and 23 weeks of gestation at Stanford Health Care. Participants will be approached during their initial consultation for abortion, after consent for the abortion has been obtained. They will sign consent and be randomized on the day of cervical preparation, one day prior to their D&E. We will use 1:1 randomization using a computer-generated variable block sequence to ensure balance of treatment groups.

We will include participants of at least 18 years of age presenting to clinic for second trimester abortion at 18 to 23 weeks and 6 days gestation confirmed by ultrasound (which will include 17 weeks and 6 days gestation on day of cervical preparation, one day prior to D&E, with or without digoxin). We will include participants who are able to provide informed consent and comply with study protocol, English or Spanish-speaking, and a candidate for outpatient cervical preparation. Exclusion criteria will include anyone with an allergy to misoprostol, mifepristone or any study medication, premature rupture of membranes, intrauterine fetal demise, placenta previa, suspected abnormal placentation or evidence of infection at the time of enrollment. Participants will be excluded on day of cervical preparation, after randomization, if their initial cervical exam is 2cm dilated and 50% effaced or more.

Participants randomized to the osmotic dilator group will receive between 2 to 5 Dilapan-S using Table 1 as guidance, depending on gestational age. Those randomized to the Foley balloon group will have a Foley catheter inserted until the balloon lies beyond the internal os that will be filled with 30 mL of sterile water or saline.

Placement of balloon or osmotic dilators will be performed in dorsal lithotomy position, with use of a speculum, standard 10-12mL paracervical block, and tenaculum or atraumatic grasper with use of adjunct initial dilation if needed (ie: os finder, sound). Adjunctive medications will be used based on our cervical preparation protocol (Table 1). Participants will receive mifepristone 200mg orally within 1 hour of osmotic dilator/balloon placement. All participants will receive misoprostol 400 ug buccal 2-3 hours prior to their scheduled D&E. Per our institutional practices, participants over 22 weeks gestation will be offered digoxin for feticide, administered upon request in earlier gestations, and use will be recorded. If the participant receives digoxin, it will be administered after dilator placement, and after the participant is asked about their pain level. Although downward traction applied to the balloon

has been associated with a shorter time to expulsion, it has been associated with more pain and bleeding.. Given these unfavorable effects, and the potential challenges of maintaining downward traction as an outpatient, initial gentle traction will be applied with the catheter taped to the participant's medial thigh; however, participants will not be instructed to maintain tension as an outpatient.

Our primary outcome will be procedure duration (speculum insertion to removal). Prior studies have demonstrated that procedure time is normally distributed with a standard deviation of 5 minutes. We will define 5 minutes as our non-inferiority threshold. To achieve 80% power with a one-sided alpha 2.5% to detect this difference, we require 16 participants per group and 32 total. Anticipating loss to follow up, we will plan to enroll 20 participants per group.

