## Description of the data to be collected and what statistical procedures will be used to answer the hypothesis and research question.

Day prior to abortion: We will collect contact information, baseline demographics and history (age, BMI, race, education, indication for abortion, parity, mode of prior deliveries, prior abortion, prior osmotic dilators, number of weeks gestation, prior cervical procedures, prior surgeries, medical problems, medications, allergies). We will record baseline pain prior to positioning patient for cervical preparation. We will collect information on initial digital cervical exam (dilation/effacement/consistency/position), time of osmotic dilator or balloon placement, number of Dilapan-S if applicable, dilator placement duration, provider ease of placement by VAS, participant reported pain after procedure (within 5 minutes of speculum removal) by VAS, reported maximum pain during procedure by VAS. If digoxin is administered, it will only be done after dilator placement and all pain levels are collected.

Day of abortion. Preoperative information will also include maximum reported pain overnight prior to misoprostol administration, time of misoprostol intake, documentation of time of osmotic dilator or Foley balloon removal or expulsion (total time with dilator in place), symptoms overnight, reported maximum pain overnight by VAS, reported number of ibuprofen and Norco pills taken overnight, patient satisfaction by VAS, and if they would recommend their type of dilation for future patients.

Abortion: We will record digital cervical exam (dilation/effacement/consistency/position), need for additional mechanical dilation, total duration of procedure (speculum insertion to removal), time from insertion of first intrauterine instrument (suction cannula or forceps) to final removal of intrauterine instrument (suction cannula), type of anesthesia, primary surgeon level (senior resident in their last half of final year, fellow, faculty), surgeon satisfaction with dilation by VAS, surgeon's ease with procedure by VAS, EBL, complications (cervical laceration, hemorrhage, perforation, infection, intact expulsion).

Post procedure: Prior to discharge, at least 60 minutes but before 120 minutes after procedure (time to be recorded), participants will be asked about overall experience by VAS, and current and maximum pain since procedure by VAS.

Table 1: Cervical preparation protocol based on gestational weeks

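### Gestational age guides the control preparation and is known before randomization, yet the plan neither stratifies nor adjusts for it

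*Combined protocol and SAP*

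**What the plan says.** The design paragraph under Protocol reads "We will use 1:1 randomization using a computer-generated variable block sequence to ensure balance of treatment groups" and names no stratification factor. The trial is described as an "unblinded, randomized, non-inferiority trial of 40 participants undergoing second trimester abortion between 18 and 23 weeks of gestation". Participants qualify "at 18 to 23 weeks and 6 days gestation confirmed by ultrasound", so gestational age is known before anyone is randomized. The baseline items in the data-collection section include it as well: "prior osmotic dilators, number of weeks gestation, prior cervical procedures".

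The two preparations treat gestational age differently. For the control arm, "Participants randomized to the osmotic dilator group will receive between 2 to 5 Dilapan-S using Table 1 as guidance, depending on gestational age". Table 1 gives 2-3, 3-4 and 4-5 dilators for its three two-week bands. The balloon "will be filled with 30 mL of sterile water or saline", with no dependence on gestational age.

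The sample-size paragraph under Protocol assumes that "procedure time is normally distributed with a standard deviation of 5 minutes". It sets a 5-minute margin, a one-sided alpha of 2.5% and 80% power, and arrives at 16 evaluable and 20 enrolled per group. The heading of the data-collection section announces statistical procedures, but the text under it lists only data items. No test, model, interval or covariate is named anywhere.

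**The concern.** Blocking keeps the arm sizes close. It does nothing to keep the arms alike in gestational age. With about 20 per arm over a six-week range, the arm means can differ noticeably by chance.

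The protocol itself treats gestational age as relevant to cervical preparation, so it is a natural candidate predictor of how long the procedure takes. If it is one, two things follow:

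- An unadjusted comparison leaves explainable variance in the error term and so gives a wider interval than necessary.
- In the one trial that is run, a chance imbalance pushes the estimate in a direction that the baseline table will show but no planned analysis will correct.

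In a non-inferiority trial, that push can decide a borderline result. Adding a covariate after the baseline table has been seen, in an unblinded trial, would look selective.

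**Working it through.** **Inputs from the sample-size paragraph:** SD 5 min, margin 5 min, one-sided alpha 0.025, 16 evaluable and 20 enrolled per group.

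**Assumptions not in the documents:** true difference 0 for power; R², the share of duration variance explained by gestational age, at 0, 0.1 or 0.3; gestational age spread evenly over six weeks for the simulation. The SD of 5 is read as the total SD.

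**Step 1. The plan's own figure.** n = 2 × [5 × (1.960 + 0.842)/5]² = 15.70, so 16 per group, as stated. Also 16/0.80 = 20. Power at 16 is 80.7% by the normal approximation and 78.1% by the noncentral t.

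**Step 2. Unadjusted comparison.** SE = 5 × √(2/n), with 2n − 2 degrees of freedom.

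- n = 20: SE 1.58, half-width of the 95% confidence interval 3.20, so the observed difference must be below 5 − 3.20 = 1.80 min. Power 86.9%.
- n = 16: SE 1.77, half-width 3.61, limit 5 − 3.61 = 1.39 min. Power 78.1%.

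**Step 3. Adjusted for gestational age.** SE = 5 × √(1 − R²) × √[(2/n) × (1 + 1/(2n − 4))], with 2n − 3 degrees of freedom. The last factor is the average price of estimating the slope.

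| R² | Power, n = 20 | Half-width, n = 20 | Power, n = 16 | Half-width, n = 16 |
|---|---|---|---|---|
| Unadjusted | 86.9% | 3.20 | 78.1% | 3.61 |
| 0 | 85.9% | 3.25 | 76.6% | 3.68 |
| 0.1 | 89.3% | 3.08 | 80.8% | 3.49 |
| 0.3 | 95.3% | 2.72 | 89.4% | 3.08 |

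Adjusted and unadjusted power are equal at R² = 0.028 (n = 20) and 0.037 (n = 16).

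**Step 4. Size of the chance shift.** The 95% range of the shift in the unadjusted difference is ±1.96 × √R² × 5 × √(2/n).

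- n = 20: ±0.98 min at R² = 0.1 and ±1.70 at 0.3, against the limit of 1.80.
- n = 16: ±1.10 and ±1.90, against the limit of 1.39.

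**Step 5. Simulation at 20 per arm** (300,000 trials per setting). The implied slopes are 0.91 min per week at R² = 0.1 and 1.58 at 0.3. Arm means of gestational age differ by at least 0.5 week in 36% of trials, that is 18% in each direction. At a true difference of 0, the adjusted and unadjusted conclusions disagree in 2.5%, 5.6% and 10.0% of trials at R² = 0, 0.1 and 0.3. The mirror cases (marked *) come from a separate run of 200,000 trials.

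| Case | Unadjusted, R² = 0.1 / 0.3 | Adjusted, R² = 0.1 / 0.3 |
|---|---|---|
| True difference 0, balloon arm ≥ 0.5 week later: power | 76% / 66% | 88% / 95% |
| True difference 0, balloon arm ≥ 0.5 week earlier: power* | 95.0% / 98.5% | 88.0% / 94.6% |
| True difference 5, balloon arm ≥ 0.5 week earlier: false non-inferiority | 6.0% / 8.7% | 2.5% / 2.5% |
| True difference 5, balloon arm ≥ 0.5 week later: false non-inferiority* | 0.6% / 0.1% | not run |

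Over all randomizations, the false non-inferiority rate is 2.5% with either method.

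**The case against.** The strongest reply is that nothing here is an error. Unstratified variable blocks are a legitimate design for 40 participants. Type I error is controlled, and the planned 20 per arm gives 86.9% power unadjusted against a target of 80%. That stands.

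The effect size is also assumed. No passage says that duration varies with gestational age, and Table 1 could even flatten such a relation in the control arm. R² = 0.3 is a strong assumption, since 1.58 × 6 is about 9.5 min across the eligible range. Below break-even, adjustment lowers power slightly. This stands too, and it is why the claim is conditional and the range starts at 0.

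The adverse imbalances have favourable mirror images that offset them on average, and some disagreement between the two analyses arises even when R² = 0. That is correct. It answers a charge of overall bias, which is not made. It does not help a reader of a single trial with a visible imbalance.

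Scaled dilators against a fixed fill could give different slopes in the two arms, which a common-slope model does not examine. Hence the descriptive report by band in the fix. Parity, BMI and surgeon level are recorded as well, and the documents rank none of them as prognostic. Gestational age stands out only because the protocol builds the control preparation on it.

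Finally, the plan states no primary analysis at all, so the unadjusted comparison is an inference about what would be done. That gap is wider than this point, and the fix below fills part of it.

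**Conclusion.** The concern holds as a conditional and inexpensive improvement, not as a flaw in validity. The plan neither balances nor adjusts for a baseline variable that it already collects and that guides one arm's preparation.

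If gestational age explains more than about 3% of duration variance (2.8% at 20 per arm, 3.7% at 16), adjustment raises power. The gain at 20 per arm is 89.3 − 86.9 = 2.4 points at 10% and 95.3 − 86.9 = 8.4 points at 30%. At the 16 evaluable per arm used in the sample size, a covariate explaining 10% moves exact power from 78.1% to 80.8%.

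Adjustment also keeps false non-inferiority at 2.5% in the imbalanced trials where the unadjusted rate reaches 6.0% or 8.7%. All of these sizes rest on the assumed R², a true difference of 0 for the power figures, and, for the simulated ones, an even spread of gestational age. The change should be made. Confidence is medium because the documents give no prognostic effect.

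**What to change.** 1. **Main change.** Pre-specify the primary analysis as a linear model of procedure duration on arm and continuous gestational age, in weeks and days by ultrasound on the day of D&E. Declare non-inferiority if the upper limit of the two-sided 95% confidence interval for balloon minus dilators is below 5 min. Report the unadjusted difference as a sensitivity analysis.
2. **Data item.** The baseline list mentions weeks only. State that days are recorded too, taken from the eligibility ultrasound.
3. **Description.** Report the arm difference by Table 1 band, without tests, so that any difference in pattern between the scaled and fixed preparations can be seen.

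The cost is about two sentences of analysis text and one degree of freedom, with no additional participants. If gestational age has no effect on duration, power falls by about 1.0 point at 20 per arm (86.9% to 85.9%) or 1.5 points at 16 (78.1% to 76.6%).

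Stratifying the block sequence is optional and is a trade-off. If it is used, keep to at most two gestational strata, conceal the block sizes, and include the stratum in the model. It needs a new list before enrolment. In an unblinded trial of 40 it also leaves more incomplete blocks and makes allocation somewhat more predictable. The covariate alone delivers the gains shown above.

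### Exclusion on a digital cervical exam comes after randomization in an unblinded trial, so the exam may be done with the allocation known

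*Combined protocol and SAP*

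**What the plan says.** The design paragraph of the Protocol section describes the study: "We will conduct an unblinded, randomized, non-inferiority trial of 40 participants undergoing second trimester abortion". On timing it says: "They will sign consent and be randomized on the day of cervical preparation, one day prior to their D&E". The eligibility paragraph then adds an exclusion that acts later: "Participants will be excluded on day of cervical preparation, after randomization, if their initial cervical exam is 2cm dilated and 50% effaced or more".

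The data-collection section, under the day before the abortion, shows that this is a digital exam and lists it ahead of device placement: "We will collect information on initial digital cervical exam (dilation/effacement/consistency/position), time of osmotic dilator or balloon placement".

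The plan describes how the 1:1 sequence is generated (computer, variable blocks). It does not say:

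- how the allocation is concealed, or when it is disclosed relative to the exam;
- who does the exam, or whether that person is masked;
- which participants form the analysis population;
- whether excluded participants are replaced, followed or analysed.

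**The concern.** Randomization protects the comparison only if leaving the analysed set does not depend on the arm. Here a participant can leave after allocation on a hands-on estimate of dilation and effacement, possibly made by someone who knows which device comes next. The numeric threshold should settle clear cases alike in both arms. Readings near the threshold leave room for judgement.

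A favourable cervix plausibly predicts a shorter procedure, and procedure duration is the primary outcome. Excluding such participants mainly from the dilator arm would lengthen that arm's mean and make the balloon look better, which favours non-inferiority. Excluding them mainly from the balloon arm would work the other way and be conservative. If exclusion does not depend on arm, the comparison stays fair and only numbers are lost.

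**Working it through.** **Inputs from the Protocol section (primary outcome and sample size).** The SD comes from "procedure time is normally distributed with a standard deviation of 5 minutes" and the margin from "We will define 5 minutes as our non-inferiority threshold". Error rates and size come from "To achieve 80% power with a one-sided alpha 2.5% to detect this difference, we require 16 participants per group and 32 total" and the reserve from "Anticipating loss to follow up, we will plan to enroll 20 participants per group".

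**The plan's own figure.** With a true difference of 0 (implied, not stated), n per group = 2 × (1.960 + 0.842)² × 5² / 5² = 15.7, rounded up to 16. Allowing 20% loss, 16 / 0.80 = 20. Both figures reproduce, so the sample size is not in dispute.

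**Arm-neutral exclusion.** Power at margin 5, SD 5 and true difference 0, by the noncentral t distribution with noncentrality √(n/2), is 86.9% at 20 per arm, 85.1% at 19, 83.0% at 18 and 78.1% at 16. The normal approximation gives 80.7% at 16. Losing one or two per arm costs little. The reserve of 4 per group is, however, attributed only to loss to follow-up.

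**Arm-dependent exclusion.** The plan has no data on this, so the following inputs are assumptions:

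- 20 are randomized per arm.
- A share p of 5% or 10% has a favourable cervix (1 or 2 per arm on average, varying at random).
- These participants are faster than the others by a gap of 1, 2, 4 or 8 minutes.

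If r is the mean of the others, the whole-arm mean is r − p × gap. Removing all favourable participants from one arm therefore raises its mean by p × gap. For p = 0.10 and a gap of 2 minutes the shift is 0.2 minutes.

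Type I error was simulated with 400,000 trials per scenario. The true balloon-minus-dilator difference was set at the 5-minute margin and the total SD held at 5. The test was a pooled t on the numbers remaining, with non-inferiority declared if the upper 97.5% limit fell below 5.

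| p | Gap (min) | Shift, one arm only (min) | Dilator arm only | 75% of dilator, 25% of balloon | Balloon arm only |
|---|---|---|---|---|---|
| 5% | 1 | 0.05 | 2.66% | 2.59% | 2.34% |
| 5% | 2 | 0.10 | 2.88% | 2.68% | 2.19% |
| 5% | 4 | 0.20 | 3.32% | 2.86% | 1.86% |
| 5% | 8 | 0.40 | 4.16% | 3.24% | 1.42% |
| 10% | 1 | 0.10 | 2.83% | 2.69% | 2.17% |
| 10% | 2 | 0.20 | 3.31% | 2.89% | 1.91% |
| 10% | 4 | 0.40 | 4.17% | 3.32% | 1.40% |
| 10% | 8 | 0.80 | 6.72% | 4.14% | 0.71% |

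With equal exclusion rates in both arms (all or half of the favourable participants), type I error was 2.45%-2.53% throughout.

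**Hand check of one cell (p = 10%, gap 2, dilator arm only).** The standard error at 20 per arm is 5 × √(2/20) = 1.58. The shift is 0.2 / 1.58 = 0.13 standard errors. The upper normal tail beyond 1.96 − 0.13 = 1.83 is about 3.3%, in line with the simulated 3.31%.

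**The case against.** The harm needs several steps that the plan does not show. The allocation must be disclosed before the exam, whereas the text says only that randomization precedes exclusion. The examiner must read borderline findings differently by arm, and no motive for that is apparent. Those borderline participants must also differ materially in duration.

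There are real safeguards as well. The criterion is a baseline one with a numeric threshold fixed in advance and common to both arms, and the exam is listed before placement, so the device is unlikely to alter the finding. Table 1 gives both arms mifepristone and misoprostol on top of the overnight device, which plausibly weakens the link between the baseline exam and duration.

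The 4 and 8 minute rows remove every favourable participant from one arm. That fits poorly with a mechanism confined to borderline readings, and 8 minutes is 1.6 of the plan's SDs. If only 2.5% of participants are borderline and the gap is 2 minutes, type I error is 2.64% with one-sided exclusion and 2.58% at 75% against 25%.

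Much of this stands as a limit on size. The 1 and 2 minute rows match the mechanism, and the larger gaps are an outer bound. It does not remove the point: the stated order permits exclusion with the allocation known, and no analysis population is defined as a backstop. Two practical objections also hold in part. The reordering is cheap but not free, and an all-randomized analysis is possible only if excluded participants have a recorded duration.

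**Conclusion.** The concern holds as a matter of design order and should be fixed. The plan places an examiner-judged exclusion after randomization in an unblinded trial and has no step that keeps the allocation hidden until the exam is recorded. Whether this would bias the result, by how much and in which direction cannot be determined from the documents.

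Under the assumptions tabulated, borderline gaps of 1 to 2 minutes put type I error at 2.7%-3.3% for exclusion from the dilator arm only, 2.6%-2.9% at a 75/25 split and 1.9%-2.3% for the balloon arm only. Gaps of 4 to 8 minutes, as a worst case, give 3.3%-6.7%, 2.9%-4.1% and 0.7%-1.9% respectively. The recommendation rests on settling eligibility before allocation when that costs almost nothing.

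**What to change.** Amend the eligibility paragraph so that the initial digital exam is done and recorded after consent and before the allocation is opened. List the existing criterion, unchanged, as a pre-randomization exclusion, delete the words that place it after randomization, and randomize only those still eligible.

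If anyone is nonetheless found ineligible after allocation, report the number and reason by arm. Present the all-randomized analysis, as far as durations exist for these participants, beside the eligible-set analysis.

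The cost is a one-sentence amendment and a change of order within a visit that already contains consent, randomization, exam and placement. Supplies for both arms must be at hand. If the exam is done once the participant is positioned for placement, the allocation has to be opened at that point. No procedure or visit is added, and the targets of 16 evaluable and 20 enrolled per group stay as they are, with the whole reserve of 4 kept for loss to follow-up.

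### Does leaving the analysis set and the missing-duration rule unstated undermine the non-inferiority conclusion?

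*Combined protocol and SAP*

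**What the plan says.** The Protocol section sets the design: "We will conduct an unblinded, randomized, non-inferiority trial of 40 participants", allocated 1:1. Later in that section comes the outcome: "Our primary outcome will be procedure duration (speculum insertion to removal"). The margin, SD, alpha and power follow and give 16 per group. The plan then adds: "Anticipating loss to follow up, we will plan to enroll 20 participants per group".

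One sentence bears directly on who is analysed, an exclusion that operates after allocation: "Participants will be excluded on day of cervical preparation, after randomization, if their initial cervical exam is 2cm dilated and 50% effaced or more".

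The next section's heading promises "what statistical procedures will be used to answer the hypothesis and research question", but its text lists data items only. It gives no analysis population, test, confidence interval or missing-data rule.

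Three other statements touch on departures from a routine course:

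- Placement may proceed "with use of adjunct initial dilation if needed (ie: os finder, sound").
- The day-of-abortion record includes "documentation of time of osmotic dilator or Foley balloon removal or expulsion (total time with dilator in place").
- The procedure record includes "complications (cervical laceration, hemorrhage, perforation, infection, intact expulsion").

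**The concern.** In a superiority trial, analysing everyone in the assigned arm is usually the cautious choice. In a non-inferiority trial it may not be. If the balloon is truly slower and some participants receive the other method, the arms look more alike and a non-inferiority claim becomes easier. Per-protocol analysis alone is not safe either: if the slower cases leave the balloon arm, the balloon looks better than it is.

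The trial is small and unblinded. With 20 per arm and SD 5, the observed difference must be below about 1.80 minutes, so how a few participants are handled could affect the verdict. A set chosen after the results are known would be open to criticism. It is therefore natural to ask whether the plan should fix the analysis set, a rule for the other method and a rule for missing durations.

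**Working it through.** **Inputs from the Protocol section.** Margin 5 min, SD 5 min, one-sided alpha 2.5%, power 80%, 16 per group, 20 enrolled per group. The documents give no rate of switching or of missing durations, so every such rate below is an assumption.

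**1. The plan's own figure.** n per group = 2(1.960 + 0.842)² × 5²/5² = 15.7, rounded up to 16. This matches the plan. A t-test calculation needs 17 (power 78.1% at 16), a minor difference. Moving from 16 to 20 corresponds to a 20% loss (1 − 16/20). With all 20 per arm analysed, t-test power is 87%.

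**2. How close the verdict can be.** Non-inferiority needs an observed difference below 5 − t × 5 × √(2/n).

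- n = 20: 5 − 2.024 × 1.581 = 1.80 min.
- n = 16: 5 − 2.042 × 1.768 = 1.39 min.

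**3. Error when the balloon truly takes 5 min longer and some receive the other method.** If c is the sum of the two arms' switching proportions, the as-randomized difference shrinks to 5(1 − c). The normal-theory error is then 1 − Φ(1.96 − 5c/1.581): 3.6% at c = 0.05, 5.0% at c = 0.10 and 9.2% at c = 0.20. Simulation (200,000 trials per scenario, pooled t, upper 95% limit below 5) gives slightly lower figures, because switching also adds spread within an arm:

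| Participants who switch (assumed) | As randomized | Per protocol |
|---|---|---|
| None | 2.5% | 2.5% |
| 1 of 20, one arm | 3.4% | 2.5% |
| 2 of 20, one arm | 4.5% | 2.5% |
| 1 of 20, each arm | 4.4% | 2.5% |
| 4 of 20, one arm | 7.8% | 2.5% |
| 4 of 20, each arm | 18.9% | 2.5% |

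Three conditions limit this table.

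- **Target.** It treats the null as a statement about the method received. If the null concerns assignment, as-randomized analysis keeps 2.5%. The documents do not state which target is meant.
- **Typical durations.** It assumes that those who switch have ordinary durations. If 2 of 20 balloon participants switch and run 5 min longer than usual, with no matching slow cases in the other arm, the as-randomized error is about 2.5%; at 10 min longer it is about 1.0%. If arm means are held equal before treatment, the 5-minute case gives 4.8%. The result depends on the model chosen.
- **Rate.** The 4-of-20 rows borrow the enrolment allowance, which the plan makes for loss to follow-up and not for switching. The last row has 8 of 40 participants receiving the other method.

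**4. Missing durations, no true difference.** The comparison is between leaving out missing balloon-arm participants and giving them a value:

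| Value given | Verdict changes, 1 missing | Verdict changes, 2 missing |
|---|---|---|
| A typical duration | 2.9% | 4.5% |
| 5 min slower than typical | 4.5% | 8.3% |
| Longest time observed in the trial | 10% | 22% |

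The longest time averages about 10.7 min above the mean, more than two SDs, so the last row is an extreme.

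**5. What a both-sets rule would cost.** With no true difference and typical participants, power when both analyses must succeed is 87% with no switching, 85% with 1 in one arm, 84% with 1 in each, about 81% with 2 in each and 76% with 4 in each. In the worst case run, 4 slower cases leaving the dilator arm, it is 64%. The rule also does not fully control the error: if 1, 2 or 4 slower cases (5 min) leave the balloon arm, false non-inferiority is 3.0%, 3.9% or 6.5%.

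**The case for a change.** The strongest case for a change is that the omission is real and not an artefact of redaction: the section that should hold the methods is present and contains none. The trial is unblinded, the allowable observed difference is small, and a few sentences written before the data are seen would remove any suspicion of choosing the set afterwards. If nobody switches, those sentences cost no power. A stated target would also settle whether the extra error in the table applies at all.

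Much of this stands as good practice, and a sponsor who writes a fuller analysis plan would do well to include it. It does not show that the plan as written leads to a wrong result. The plan nowhere says that it will rely on as-randomized analysis alone, so the extra error belongs to an assumed reading. Nor do the documents provide for switching: the os finder or sound helps to place the assigned device, and recording removal or expulsion gives time in place. Neither is receipt of the other method. The allowance of 4 per arm shows that the sponsor expects some loss, but the primary outcome is measured one day after randomization, so missing durations may be few.

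**Conclusion.** No change to the plan follows. This is missing detail that analysts fill sensibly, not an error in a stated rule. The ordinary reading of a randomized comparison is that participants with a recorded duration are analysed in their assigned arm, after the cervical-exam exclusion, with a per-protocol result and counts by arm beside it. The placement items already listed, including the number of osmotic dilators, largely show which method was used.

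For small numbers of participants switching in one arm (1 or 2 of 20, assumed, with typical durations), the error at the margin is about 3.4% or 4.5% instead of 2.5%, and only if the target is the effect of the method received. With one or two missing durations of typical length, the verdict changes in about 3% or 4.5% of trials. The larger figures (18.9% error, and 10% or 22% verdict change) rest on a borrowed loss allowance applied to both arms, or on an extreme imputation.

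The one remedy that would alter the trial's decision rule, requiring success in both sets, trades power for partial protection. That choice is the sponsor's, and leaving it out is not a fault.
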